# 9. STUDY PROCEDURES (AIM 2)

**Aim 2:** The goal of this aim is to assess the acceptability, appropriateness, feasibility, and efficacy of Social-LEAF. We will conduct a pilot randomized controlled trial of the Social-LEAF intervention in 60 subjects (30 intervention; 30 waitlist control) and use mixed methods to assess feasibility, acceptability and efficacy.

- Aim 2 Procedures: Subjects will complete six, weekly, 90 minute group sessions of the Social-LEAF intervention. Subjects enrolled in the study will be randomly assigned into either an immediate intervention group or a waitlist control (receives intervention after 6 weeks) by a computer program. Subjects will know which arm they will be in after enrollment in the study. The intervention will be delivered completely online. We ask that subjects find a nice and quiet area in which there is minimal distractions to conduct these visits. Subject privacy is very important to us. Subjects will be asked to complete a daily emotion check-in (5 minutes) during the 6week course period. This will be delivered to them via Redcap as a survey as well. Prior to beginning the Social-LEAF course, they will receive a computer tablet to use for the study, if they express the need for it. Subjects will also be asked to complete our online outcome measures at each data collection point (3 total) approximately every 6 weeks (baseline, week 6, and week 12) after you are officially enrolled in the study. The total time to complete these activities in one day is approximately 2 hours and 15 minutes. Please refer to Table 4 for a list of these measures. Furthermore, if the study research coordinator sees anything concerning (I.e., signs of abuse, selfharm, etc.) during the duration of a research visit, then there are measures in place to address this. These measures include contacting the PI and chaplain immediately, relaying these concerns, and gathering as much information as possible before taking action towards this concern. There will be 3 groups of 10 (on average; this number may range from 5-15 depending on randomization, recruitment and retention) that will be in each group (intervention or control). Each group of subjects will go through the study procedure together. Data from subjects in all groups will be collected at baseline, week 6, and week 12. Data collection will happen via zoom/via Redcap survey sent to them by the email subjects initially provide the coordinator with. The waitlist control subjects will start the intervention at week 6 but still complete the measures for data collection at baseline, week 6 and week 12. Table 3 displays the timeline in which the study procedures for Aim 2 will take place. Planned deliverables from this aim will include a final intervention manual, a manuscript on the pilot intervention, and pilot data suitable to pursuing future grant opportunities.
- Quantitative Survey Outcome Measures: Our primary outcome measure is the PROMIS Positive Affect Scale. We will also be assessing the Positive Aspects of Caregiving scale (positive consequences of caregiving) and other measures of caregiver distress and wellbeing (see Table 4). These measures will be administered at each data collection point mainly via Redcap as a survey, and/or via the study

coordinator administering it as required by the scale. The health history data will be collected when the subject initially consents, and updated as the study progresses. Altogether, the duration to complete these measures altogether is roughly 2 hours and 15 minutes.

**Table 3. Aim 2 Procedures Timeline** 

	Intervention	Waitlist Control
Baseline	Data collection point, Start online LEAF procedures	Data collection point
Week 6	Data collection point	Data collection point, Start online LEAF procedures
Week 12	Data collection point (maintenance)	Data collection point

#### **Table 4. Outcome measures**

Demographics (Baseline)	UCLA Loneliness, short form
Modified Barthel Index (Baseline)	Perceived Stress Scale (PSS-10)
FAST (Baseline)	Positive Aspects of Caregiver scale
PROMIS social isolation	Berkman-Syme Social network
PROMIS satisfaction w/ roles and activities	Modified Caregiver Strain Index
PROMIS depression	SF-14
PROMIS anxiety	Montgomery Borgata Caregiver Burden Scale
PROMIS Positive Affect Scale	UCLA Loneliness, version 3
NPI-Q	Differential emotions scale

- Aim 2 Feasibility and Efficacy Outcomes: We will utilize the RE-AIM framework to assess feasibility including: % of subjects approached who join the study (**Reach**); change in survey results (**Efficacy**); % of subjects who complete all intervention activities (**Adoption**); fidelity of facilitators to the manual as written (**Implementation**); and % of subjects who continue to engage in these skills 6-weeks following the intervention (**Maintenance**).
- Aim 2 Interviews and Value Proposition Design: We will conduct a semi-structured end of study interview with select subjects at the completion of the study to understand their perspectives on whether the intervention was beneficial, how it impacted their personal and social lives, and how it was received by others in their social network. Additionally, we would like to receive feedback on what specifically worked for them and what areas they would personally modify. To understand opportunities for any further improvements we will follow customer discovery and value proposition design guidance and materials from Osterwalder et al.  This framework allows us to gain greater depth into the perceived "jobs, pains, and gains, of daily care partner and features of the intervention and related social support that serve as "gain creators and pain relievers." Care partners will undergo a single, brief and focused interview at the end of the study to see whether and where they noticed any changes in social interactions with the primary subject and whether they have suggestions for further improvement.
- Analysis: Our primary analyses of surveys and data will be descriptive with particular attention paid to feasibility and to which scales appear most and least responsive to

the intervention. Secondary quantitative analyses will explore mechanisms and qualitative analyses will be used to gain further insights into how Social-Leaf benefits care partners, what outcomes are most meaningful and whether further adaptations are needed.

**Demographic data** will be obtained by the URMC project study coordinator after study subjects have provided their consent to participate. The information will be provided by subjects via Zoom and/or REDCap survey sent to their email. The demographic information will be documented in the University of Rochester's REDCap system.

**End of study interview** will be conducted by the URMC project study coordinator who is trained in interview techniques. Subjects will be scheduled for a video interview via Zoom based on their choice and convenience. Interviews will be conducted at a time convenient to the subject, will be audio-recorded using Zoom connected to a URMC-approved HIPPA-compliant account. Interviews with the research coordinator will typically last approximately 30-45 minutes.

Interview questions will focus on recognizing that people have the capacity to experience positive emotion even in the midst of distressing circumstances, identifying recent positive events and things to be grateful for, having a basic understanding of gratitude and the potential benefits it might have, etc.

The interview will be audio recorded so that the full conversation can be transcribed for later analysis, and subjects will be informed of this before the discussion begins. No identifying information (for example, subject names, or other personal details shared during the discussion) will be included in the transcript.

# **Return of Research Results**

As part of this study, we may learn information relevant to subject. If this happens, we will provide them information that would be relevant once the study is complete. Subjects will be given the option at the end of this consent to decide if they would like to receive these relevant results. For the interpretation of these results, we strongly recommend subjects contact their primary care physician.

Some things subjects should know about results:

- Sometimes the meaning of the results will be uncertain. It is important to know that our understanding of health is changing quickly, and in many cases, we may not know for sure what the results mean for a subject's future health.
- Any results we return to subjects will first be verified by the PI.

#### 10. AUDIO/VIDEO RECORDINGS

A URMC-approved HIPPA-compliant zoom account will be used to conduct the recording of the interviews. Recordings of interviews will be deleted from the recording

devices once the recordings are transferred from the recording devices to Landmark Associates for transcription. All recordings will be transcribed and the transcription will be kept for three years following the completion of the study and then destroyed. Subjects can request to have these recordings destroyed at any time. Interview recordings will be transcribed by Landmark Associates, a transcription company that has been approved and vetted by the University of Rochester IT Security. All files transmitted or stored in their system are protected by multiple layers of encryption through Amazon's S3-managed encryption keys (SSE-S3). With SSE, every file is encrypted with a unique key, which is also encrypted by a separate master key which rotates regularly. The encrypted data, encryption keys and master keys are stored and secured on separate hosts for additional layers of protection. In addition, Landmark internally implements two-factor authentication for administrative users, which adds an additional safeguard in the login process. Login attempts that do not have the valid credentials from both sources are not granted access to the system. In addition, Landmark implements IP restrictions, preventing those who try to login to their system outside the designated IP address to gain access. Each employee, executive staff member and contractor of Landmark is required to sign a non-disclosure and confidentiality agreement, and follow Landmark's security policies.

#### 10. RISKS TO SUBJECTS

For the majority of study activities (which include the qualitative/quantitative measures, the intervention, and the interview) the primary risk is mild reactions of distress or fatigue or is invasion of privacy, and/or breach of confidentiality (if safety issues are detected). It is possible that conversations around certain conditions, telehealth, or support needs could cause distress or anxiety. The URMC project study coordinator is trained to recognize potential signs of fatigue and distress among subjects and is experienced in coordinating the interviews. During the course of the semi-structured interviews, the researcher will listen for signs of fatigue and will offer subjects a break from the interview, or provide them with the option to complete the interview over several sessions if needed. If subjects express or demonstrate signs of distress, they will have the option to decline answering a question. There is the possible risk of unauthorized release of interviews that could result in release of private information. All and every effort will be made to minimize any breach of data and ensure that all data are de-identified. There is potential risk of signs of depression and suicidal ideation. If the study team finds a subject exhibiting these characteristics, they will address this immediately by contacting the chaplain. The research study coordinator will ascertain their risk by their responses to questionnaires and their overall discretion on how the subject is interacting with them. They will contact the PI and /or chaplain for immediate assistance/guidance to develop a plan to address the issue. Lastly, if the study team learns that you or someone with whom you are involved is in danger or potential harm, such as elder abuse they will need to inform, as required by New York State law, the appropriate agencies.

#### 11. POTENTIAL RISK TO SUBJECTS

Fatigue, stress, topics that may be saddening, conversation about these topics, invasion of privacy, etc.

### 12. POTENTIAL BENEFITS TO SUBJECTS

There are no anticipated benefits.

#### 13. COSTS FOR PARTICIPATION

None anticipated

#### 14. PAYMENT FOR PARTICIPATION

Subjects will receive \$25 for successfully completing the individual interview for Aim 1. For Aim 2, they will receive \$25 for the completion of each data collection point associated with the study. This includes baseline, week 6, and week 12, for a total of \$75. Individuals who express interest and are chosen to do the post-intervention interview will receive \$25 as well, which can will total their compensation to \$100.

#### 15. SUBJECT WITHDRAWALS

Subjects are free to withdraw at any time without negative consequences. Subjects may also refuse to answer any individual questions. If a subject voluntarily withdraws from the study, we will attempt to the note the reason if provided by the subject. We will use the data already collected up until the point in which the subject decides to voluntarily withdraw from the study. In the event of the latter, subjects who withdraw from the study will be replaced.

#### 16. PRIVACY AND CONFIDENTIALITY OF SUBJECTS AND RESEARCH DATA

We are requesting altering HIPAA authorization so as to obtain permission during the verbal consent process to gather subjects' demographic data.

- Elements of authorization are being altered
- Without subjects' phone, email, and home address the study data collection and the mailed check for participation cannot be completed. Other demographic data such as race/ethnicity are important to answering the study research questions as they will facilitate an understanding of the challenges, barriers, and supports experienced by different subjects.
- The demographic data being gathered are no more than minimal risk to the privacy of the individuals
- All identifying information will be maintained on the REDCap system at the University of Rochester and printed copies of subject's names, email, and home addresses will be held by the URMC project study coordinator in a locked cabinet in her office at the University of Rochester and on an encrypted University of Rochester computer. All identifying information will be destroyed three years after the completion of the study.
- PHI will not be reused or disclosed to any other person or entity except (i) as required by law, (ii) for authorized oversight of the research study, or (iii) for other research for which the use or disclosure of PHI would be permitted by the HIPAA Privacy Rule.

In order to protect the confidentiality of subject information, we will take a number of precautions. All data will be securely stored and maintained according to the regulations of privacy stipulated by the University of Rochester. All data will be held by the URMC

project study coordinator in a locked cabinet in her office at the University of Rochester and on an encrypted University of Rochester computer. Audio recordings of semi-structured interviews will be transcribed and then kept three years following the completion of the study. Demographic information and de-identified transcripts will be stored on an encrypted, password protected computer and will be accessible only to the study PI and study team members. Back-ups of all study files will be made daily to allow for recovery of data due to disk failure. Confidentiality will be further maintained by the storage of "hard copy" data in locked files in a locked office. Only the research team and approved study personnel will have access to the data. All data reported in presentations or publications will be de-identified and will report only cumulative data or descriptions certain to maintain subjects' anonymity.

# 15. DATA / SAMPLE STORAGE FOR FUTURE USE

N/A

## 16. DATA AND SAFETY MONITORING PLAN

N/A

# 17. DATA ANALYSIS PLAN

Qualitative analyses (Aim 1) will use Atlas.ti software for coding and an inductive approach. We will iteratively modify materials alongside interviews and will plan to pilot our group approach in single sessions of several modules to troubleshoot materials before finalizing pilot materials for Aim 2. For qualitative analyses in Aim 2, to understand opportunities for any further improvements we will follow customer discovery and value proposition design guidance and materials from Osterwalder et al.

For Quantitative analyses (Aim 2), our primary analyses of surveys and data will be primarily descriptive with particular attention paid to feasibility and to which scales appear most and least responsive to the intervention. Secondary quantitative analyses will explore mechanisms and qualitative analyses will be used to gain further insights into how Social-Leaf benefits care partners, what outcomes are most meaningful and whether further adaptations are needed. With 60 subjects we will be able to detect large between-group differences (0.7 SD/mean) and modest pre/post differences (0.5 SD/mean), which fall within the range of the original LEAF results.

Title: Social-LEAF Life Enhancing Activities for Caregivers

NCT05274074 Date: 1.9.25 Analysis will be intent to treat. We will examine balance of demographic and outcome measures across groups at baseline using chi-square tests for categorical variables and t-tests for continuous variables. For cell frequencies less than 5 fisher's exact test will be used and for continuous variables with heavy skew Kruskal Wallis tests will be used.

The primary analysis assessing intervention effects will be conducted with general linear models comparing the change from baseline to the week 6 visit by group. Model specification will include change from baseline to week 6 for each measure as the outcome and group as the independent variable. Within group change will be estimated as least squares means with corresponding 95% confidence intervals.

PROMIS instruments administered via a computer adaptive test will be analyzed on the T-score metric provided by the computer adaptive testing administration. Those scores are normed on a national sample, in which they have a mean of 50 and standard deviation (SD) of 10. For the remaining instruments including the primary outcome PROMIS Positive Affect, raw scale scores will be analyzed. Differences between the change from baseline and the week 6 visit in each group will describe effect sizes. Higher scores indicate higher values of the construct being measured by the instrument (i.e. higher PSS scores indicate higher stress, higher PROMIS depression scores indicate higher depression).

Statistical tests will be 2-sided F-tests with an alpha of .05 comparing the intervention and waitlist control on change from baseline to week 6 for each outcome. All analyses will be based on actual data and no imputation of missing data will be performed. Given the small sample size, lack of power, and preliminary nature of the study, no formal adjustments will be made for multiple comparisons.

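### The SAP's only effect size is in each scale's own units, so it does not serve the protocol's question of which scales respond most; a prespecified standardised difference with a confidence interval would.

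*SAP*

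**What the plan says.** **Protocol.** Section 17 (Data Analysis Plan) describes the Aim 2 quantitative analyses as "primarily descriptive with particular attention paid to feasibility and to which scales appear most and least responsive to the intervention". The Analysis item in Section 9 says nearly the same. Section 17 also states what 60 subjects can detect: 0.7 between groups and 0.5 pre/post. The unit is written as SD/mean and is read here as SD units. Table 4 has 18 entries; three are marked as baseline only, which leaves 15 repeated measures.

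**SAP.**
- Model: "Model specification will include change from baseline to week 6 for each measure as the outcome and group as the independent variable". Within-group change is to be reported as least squares means with 95% intervals.
- Metric: "PROMIS instruments administered via a computer adaptive test will be analyzed on the T-score metric provided by the computer adaptive testing administration", with a norm SD of 10. Then: "For the remaining instruments including the primary outcome PROMIS Positive Affect, raw scale scores will be analyzed".
- Effect size: "Differences between the change from baseline and the week 6 visit in each group will describe effect sizes". I read this as the between-group difference in change. No SD is named as a divisor.
- Direction: "Higher scores indicate higher values of the construct being measured by the instrument", illustrated by the stress scale and PROMIS depression.
- Tests: "Statistical tests will be 2-sided F-tests with an alpha of .05", one for each outcome.

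**The concern.** Asking which scales respond most and least is a comparison between scales, and it needs a common unit. The effect size that the SAP defines has none. Even within the PROMIS family the unit is mixed, because Positive Affect is analysed raw while the adaptively administered scales are T-scores. A point on one instrument is not a point on another.

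Two further gaps matter. Intervals are promised for change within each arm but not for the difference between arms, which is the quantity of interest. And where no standardiser is fixed in advance, anyone who standardises later must choose one after seeing results, and that choice can change the order of the scales.

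At stake is the use of the pilot. It is meant to lay the ground for later trials, and the choice of outcome measure is one of the things it could inform.

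**Working it through.** **Inputs.** 30 per arm (protocol Section 9). Two-sided alpha 0.05, with group as the only model term (SAP). T-score norm SD 10 (SAP). The documents give no SD of change for any scale and no correlation r between baseline and week 6; the values used below are assumptions for illustration.

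**1. The protocol's own figure.** No power is stated, so 0.7 cannot be strictly reproduced. At 80% power the detectable difference is (1.96 + 0.842) × √(2/30) = 0.72 SD by the normal approximation, or 0.74 SD by the t distribution. Both round to 0.7. Power at exactly 0.7 SD is 77.4% (normal) or 76.0% (t). This supports reading the protocol's figures as SD units. It does not settle the present point.

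**2. Native units do not order the scales.** With d = difference / SD of change, and F = d² / (2/30) = 15d²:

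| Assumed SD of change | d for a 3-point difference | F | Points equal to 0.7 SD |
|---|---|---|---|
| 3 | 1.00 | 15.0 | 2.1 |
| 5 | 0.60 | 5.4 | 3.5 |
| 10 | 0.30 | 1.35 | 7.0 |
| 15 | 0.20 | 0.60 | 10.5 |

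The same 3 points span a fivefold range of standardised effect. The order can also reverse. If the SD is 10, 5 points are 0.50 SD; if it is 4, 3 points are 0.75 SD, the smaller number but the larger effect.

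**3. What the planned output already contains.** With two groups and no covariate, F = t², so |d| = √F × √(1/n₁ + 1/n₂). At 30 per arm √(2/30) = 0.258, so F = 1, 4 and 7.35 give |d| = 0.26, 0.52 and 0.70. The sign comes from the least squares means.

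**4. The divisor matters.** The d from F divides by the SD of change. Assuming equal variances at the two visits, SD of change = baseline SD × √(2(1 − r)), so the d from F equals the baseline-SD version times 1/√(2(1 − r)). That factor is 0.85 at r = 0.3, 1 at r = 0.5 and 1.58 at r = 0.8. Suppose one scale shows 0.5 baseline SD with r = 0.8, and another 0.7 baseline SD with r = 0.3. In SD-of-change units they become 0.5 × 1.58 = 0.79 and 0.7 × 0.85 = 0.59. The order flips.

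**5. Precision.** Dividing by the SD of change, SE(d) ≈ √(2/30 + d²/120): 0.258 at d = 0, 0.262 at d = 0.5 and 0.266 at d = 0.7. The 95% half-width is 1.96 × SE, or 0.51 to 0.52. Dividing by the baseline SD, the leading term is 0.506 × √(2(1 − r)): about 0.60 at r = 0.3, 0.51 at r = 0.5 and 0.39 at r = 0.7.

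**The case against.** The best reply is that nothing is missing except a column in a table. Step 3 of the working recovers the size of d from F, and the sign follows from the arm means and the stated scoring direction. The between-arm interval can be rebuilt as well, since the standard error is |difference| / √F. The SAP analyses each measure separately and tells no one to compare raw points across instruments. The protocol speaks only of which scales appear responsive, promises no formal ranking, and names feasibility first. The SAP itself concedes that the study is small and underpowered.

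Most of this stands, and it rules out several stronger readings that a reader might infer:

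- *That the trial could not show relative responsiveness.* The planned output holds the information; the SAP does not plan the summary.
- *That responsiveness is the sole primary quantitative purpose.* It is named alongside feasibility.
- *That opposite good directions block comparison.* The SAP states the scoring direction, so a sign convention is enough.
- *That the primary result cannot be set against the protocol's 0.7 SD, or misses a target.* The 0.7 is a detectable difference, and F converts to that kind of unit.
- *That raw-scored scales will look systematically less responsive than T-scores.* That depends on SDs that the documents do not give; with a raw SD above 10 it goes the other way. The 10 is also a national norm, not this sample's SD.

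The reply does not answer the choice of divisor. It is left open and can alter the order. Nor does it change the fact that the one effect size the SAP names is not the one the protocol's question needs.

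**Conclusion.** The point holds as a mismatch between the protocol's question and the SAP's stated summary measure. Native-unit differences in change are not comparable across the 15 repeated measures, no standardiser is fixed, and no between-arm interval is promised. It should be corrected, but it is not a loss of data or a fault in the planned tests.

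Its size can only be illustrated. Over an assumed SD of change of 3 to 15 points, one 3-point difference ranges from 1.00 to 0.20 SD. The half-width of about 0.5 SD assumes 30 analysed per arm, division by the SD of change, and independent observations (no allowance for delivery in groups). With no imputation planned, dropout would widen it. With a baseline SD as divisor it depends on r, which is unknown. Standardising makes the scales comparable; it does not make their order precise.

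**What to change.** Keep the native-unit difference and add to the SAP:

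1. For every outcome, report the between-arm difference in change from baseline to week 6 divided by one prespecified standardiser. Either the pooled baseline SD or the SD of change from the planned model would do; name one and use it throughout.
2. Sign it so that positive means benefit, and list for each scale the metric used and the direction of benefit.
3. Give a 95% CI for the between-arm difference, both in native units and standardised, with the latter computed for the chosen standardiser.
4. Describe relative responsiveness from this figure together with its interval, and state in advance that at 30 per arm the half-width is about 0.5 SD if the SD of change is the divisor, so any ordering is imprecise.

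The cost is SAP wording, one extra table column and a decision on the standardiser. No new data are needed, and the design and the planned tests are unchanged.

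### The analysis is called intent to treat, but an unadjusted change score with no imputation makes it a complete-case comparison, biased if loss by week 6 depends on baseline score and differs by arm

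*SAP*

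**What the plan says.** The SAP has no numbered sections. It opens with "Analysis will be intent to treat" and does not define that set further. Its primary model is specified as follows: "Model specification will include change from baseline to week 6 for each measure as the outcome and group as the independent variable". No baseline covariate and no repeated-measures model are mentioned. On missing data it says "All analyses will be based on actual data and no imputation of missing data will be performed". On scoring, apart from the PROMIS scales given by computer adaptive test, it says "For the remaining instruments including the primary outcome PROMIS Positive Affect, raw scale scores will be analyzed". It gives no rule for a partly answered scale and plans no missing-data sensitivity analysis.

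Protocol section 15 (Subject Withdrawals) makes three relevant statements:
- On skipped items: "Subjects may also refuse to answer any individual questions".
- On data from withdrawn subjects: "We will use the data already collected up until the point in which the subject decides to voluntarily withdraw from the study".
- On replacement: "subjects who withdraw from the study will be replaced".

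Protocol section 17 (Data Analysis Plan) gives detectable differences of 0.7 SD between groups and 0.5 SD pre/post with 60 subjects. It makes no allowance for loss.

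**The concern.** The label and the model do not match. Intent to treat promises a comparison of everyone randomised, in the arm assigned. The model can use only those scored at both visits. A subject who withdraws before week 6 has retained data that contribute nothing to the primary comparison, and is then replaced by someone else.

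Loss that differs by arm is plausible. Under Protocol section 9, subjects know their arm after enrolment, and between baseline and week 6 only the intervention arm attends six weekly 90-minute sessions. If more distressed care partners leave that arm, the remaining subjects differ from the waitlist at baseline, and an unadjusted change score does not correct for this. The pilot is meant to supply effect sizes for grants and later trials, so a mislabelled and possibly biased estimate would be carried forward.

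**Working it through.** **1. The plan's own figure.** Inputs are 30 per arm (Protocol section 9) and two-sided alpha 0.05 (SAP). Power is not stated; I assume 80%. By the normal approximation:
- Between groups: (1.960 + 0.842) × √(2/30) = 0.723 SD.
- Pre/post within one arm: (1.960 + 0.842)/√30 = 0.511 SD.

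These round to the stated 0.7 and 0.5, so the figures fit 80% power with all 60 subjects evaluable. At exactly 0.7 SD, power from the two-sample t-test is 76%.

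**2. Who enters the model.** Change = week 6 − baseline.

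| Baseline | Week 6 | In primary model? |
|---|---|---|
| scored | scored | yes |
| scored | missing | no |
| missing | scored | no |

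With no imputation, the analysed set is the first row only.

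**3. When this biases the estimate.** Let β be the slope of week 6 on baseline, the same in both arms, and let loss depend only on arm and baseline. Among completers, expected change moves by (β − 1) for each unit of baseline. Let m be the completers' mean baseline minus the mean of all randomised. Then

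bias = (β − 1) × (m_intervention − m_control).

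It is zero if loss is unrelated to baseline, or if its pattern is the same in both arms.

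Illustration, all inputs assumed: 20% of the intervention arm is lost, those lost average 0.8 SD below their arm at baseline, and no waitlist subject is lost. Then m_intervention = (0.20/0.80) × 0.8 = 0.20 SD.
- β = 0.5: bias = −0.5 × 0.20 = −0.10 SD.
- β = 0.3: bias = −0.7 × 0.20 = −0.14 SD.
- β = 0.7: bias = −0.3 × 0.20 = −0.06 SD.

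A separate simulation, with about 17% assumed loss dependent on baseline and arm, also gave a mean bias of −0.10 SD for the change score. The baseline-adjusted model had bias of about 0 and a smaller standard error.

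**4. What a joint model does.** Model baseline and week 6 together, with a common baseline mean μ₀ and a common covariance. The likelihood splits into baseline, and week 6 given baseline and arm: E(week 6) = a + τ·arm + β·baseline. The difference between arms at week 6 is (a + τ + βμ₀) − (a + βμ₀) = τ. Subjects without week 6 inform only μ₀, which cancels. So when the missing values are all at week 6, τ equals the completers' ANCOVA estimate. In one simulated data set both gave 0.3816, against 0.4692 for the change score. The gain is validity under loss that depends on baseline and arm, and usually precision; no subjects are recovered for power.

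**5. Power if subjects are lost.** For an assumed 20% loss, 30 × 0.8 = 24 per arm. Two-sample t power at 0.7 SD falls from 76% to 66% (77% to 68% by the normal approximation).

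**The case against.** The strongest reply is that this is a pilot. The protocol calls its quantitative analyses primarily descriptive, and the SAP concedes low power and a preliminary purpose. Nothing in the documents shows that loss will differ by arm. Replacement also offsets lost numbers, so the fall in power may not occur. All of this stands, and it limits the stakes. It does not remove the mismatch, because the SAP still specifies a primary between-arm test at 0.05 under a label its model cannot deliver. Replacement restores the count but not the set that was randomised.

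Two stronger readings are tempting, and the documents support neither.

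**One skipped item removes a subject.** Refusal is allowed, raw scores are used and imputation is ruled out, so a reader might infer this. But the SAP does not say how a partly answered scale is scored. The no-imputation rule may concern whole visits only, and survey settings or instrument scoring rules could govern the rest. With 8 to 15 items and 1% refusal per item, 1 − 0.99^(2k) gives 15% to 26% of subjects with a gap at either visit. Form length, refusal rate and independence of skips are all assumed there. At the same refusal rate, an assumed within-person correlation of 0.1 brings it down to 9% to 13%. What the documents do show is that no item-level rule is stated.

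**A repeated-measures model restores a full intent-to-treat analysis with all 60 subjects' information.** Step 4 of the working shows that it does not. For a missed week 6, inclusion is nominal as far as the group effect is concerned.

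**Conclusion.** The point holds. As specified, the primary analysis is complete-case by randomised arm under an intent-to-treat label; this follows from the SAP text and needs no assumption. Bias is conditional: it arises if loss by week 6 depends on baseline score and differs by arm. In the assumed illustration it is 0.06 to 0.14 SD, against the 0.7 SD the protocol hopes to detect. The documents give no missingness rate, form length or item refusal rate, so the bias and power figures show scale only and are not predictions. The absence of a rule for partly answered scales is a secondary gap. For a pilot this should be corrected, but it does not undermine the design.

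**What to change.** 1. Replace the unadjusted change-score model with a likelihood-based model of baseline and week 6 that has a common baseline mean. Where only week 6 is missing, this is equivalent to ANCOVA on baseline. State that it is valid when missingness depends on observed baseline and arm, and that it does not recover power from baseline-only subjects.
2. Describe the analysis as all randomised subjects by assigned arm under missing at random. Keep withdrawn subjects in their arm alongside any replacements, and report missingness by arm.
3. State that the no-imputation rule does not bar prorated scoring of a partly answered raw scale when at least half its items are answered.
4. Keep the planned complete-case change analysis as a sensitivity analysis.

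The cost is a few sentences in the SAP and one standard model per outcome, with no new data. The small downside is reliance on missing at random, which the data cannot verify.
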